5.10 Storage and Accountability

Bexagliflozin tablets will be stored at controlled room temperatures of 15°C to 30°C (59°F to 86°F). The rescue medications will be stored in conditions specified in the manufacturers' prescribing information. The sponsor will notify the sites of the process for returning unused drug.

5.11 Investigational Product Retention at Study Site

The investigational products should be stored in a secure area with limited access at controlled room temperature until ready for dispensing to study subjects. The drug storage facility must comply with the medication storage instructions. The trial staff must record the amount of investigational product dispensed to each subject on the dosing record. To ensure

adequate recordkeeping, subjects must bring all investigational products to each visit. The remaining tablets will be accounted for in the CRF and drug consumption forms. The procedures for obtaining drug resupply will be provided by the sponsor. At the completion of the trial, all unused drug must be returned to a sponsor-designated depot after drug accounting is verified by the sponsor or its designee.

6 STUDY PROCEDURES

6.1 Informed Consent

All subjects will be informed of the nature and purpose of the study and their written informed consent will be obtained during the pre-study screening procedures. A copy of the informed consent forms, including subject information, will be provided to each subject. The investigator must educate potential subjects about the scientific importance of their data and the vital role that their participation has for the outcome of the entire study.

6.2 Medical History

The following information will be collected at the screening visit:

6.2.1 General Demographics and Characteristics

1. Date of birth, age, sex, and race, and whether a female subject is of childbearing potential or not
2. Significant medical and surgical history, including dates of diagnoses and procedures and whether the condition is ongoing, if applicable.

6.2.2 Diabetes History

1. History of all medications used to treat diabetes (to be recorded in the concomitant medication form), including start date, duration of use, and stop date, if applicable.
2. History of complications due to diabetes, including nephropathy, retinopathy, neuropathy, non-traumatic amputations, and diabetic ketoacidosis, including date of diagnosis
3. Frequency of hypoglycemic events (per week) that are symptomatic or require assistance.

6.2.3 Cardiovascular Disease History

History of cardiovascular disease including presence of angina, congestive heart failure (classification, if present), known atherosclerotic cardiovascular disease, prior MI, cerebrovascular ischemia (TIA or stroke/cerebrovascular accident) and prior cardiac or peripheral re-vascularization procedures.

History should include date of diagnosis and current status of diagnosis (resolved or ongoing).

6.2.4 Medication History

1. Use of prescribed or non-prescribed medications, including name of medication, indications for usage, start and stop dates, dose, and frequency
2. Use of supplements, including over the counter drugs, vitamins, herbal medicine, and dietary supplements within the past 30 days prior to screening. A medication history will

include the medication used, indication for usage, start and stop dates, dose, and frequency.

6.3 Physical Examination

A complete physical examination will be performed by the investigator at screening and at the last study visit. A complete physical examination will include measurement of body weight and height (height will be measured only at screening), general assessment of all body systems including the skin, head, eyes (including fundoscopic exam), ears, nose, throat, neck, heart, lungs, abdomen, lymph nodes, and extremities (including Achilles tendon reflex and foot exam). The fundoscopic examination should be characterized as normal or abnormal with description of any detected abnormality. The Achilles tendon reflex should be graded as normal or abnormal. The foot exam should assess skin and toenail lesions and be documented as normal or abnormal with description of any detected abnormality.

An abbreviated physical examination will include general assessment of the skin, heart, lungs and abdomen. Abbreviated physical examinations will be performed by the investigator at all other time points as defined in the Schedule of Events, unless clinically indicated.

The body weight must be determined at clinical visits specified in the Schedule of Events (Appendix 1) using a scale that is calibrated regularly.

6.4 Vital Signs

Vital signs will be measured as indicated in the Schedule of Events ([Appendix 1](#)) and will include supine, sitting and standing blood pressure (BP) measurements, pulse, temperature and respiratory rate.

6.4.1 Blood Pressure and Pulse Measurements

Devices designed to measure BP from the finger or wrist may not be used. The left arm and same cuff sizes should be used for each measurement at all visits. If the left arm cannot be used for BP measurements, the reason should be documented, and the right arm should be used for BP measurements at all study visits.

At each visit, BP measurements will be obtained using a calibrated sphygmomanometer while the subject is in sitting, supine, and standing positions. A single pulse measurement should be taken just prior to the BP evaluation in the sitting, supine, and standing positions.

All readings are to be entered into the source document and CRF for all subjects. The date and time of BP measurements should be captured in the source document and CRF. BP will be assessed first in the sitting position. Sitting BP and pulse will be measured after the subject has been sitting for at least 5 minutes with feet on the floor and arm supported at heart level.

After sitting BP measurement has been completed, supine and standing BP will be measured to evaluate orthostatic vital signs. Supine and standing blood pressure measures will not be

used to determine eligibility for the study. First, the subject will lie flat for 5 minutes and have pulse and supine blood pressure measured using the same equipment and arm as described for sitting BP. Once the supine BP measurement is complete, the subject will stand. Standing BP and pulse will be measured after 2 minutes of standing. For standing BP measurements, the arm should be supported and extended such that the cuff is at heart level.

6.4.2 Temperature and Respiratory Rate

Oral, axillary, or ear temperatures are acceptable but they must be taken from the same measurement site during the study. The subject should be advised to rest after strenuous physical activity prior to a temperature measurement. When taking the temperature orally, the subject must not have eaten, drunk, or smoked anything in at least the previous 15 to 20 minutes, as the temperature of the food, drink, or smoke can dramatically affect the reading.

Respiratory rate should be measured after at least 5 minutes of rest.

6.5 Electrocardiography

A 12-lead electrocardiogram (ECG) will be conducted as listed in the Schedule of Events in [Appendix 1](#) and whenever clinically indicated. This procedure should be performed in the supine position after at least 10 minutes of rest. ECG parameters measured will be the RR interval, PR interval, QRS duration, and QT, P-wave axis, and QRS-axis. Each ECG should also be assessed by the investigator for signs of ischemia, clinically significant hypertrophy, and clinically significant T-wave abnormalities.

It is the investigator's responsibility to review the results of the ECG as they become available. For each abnormal ECG result, the investigator needs to ascertain if this is a clinically significant change from the screening ECG for that individual subject (this determination, however, does not necessarily need to be made the first time an abnormal result is observed. The investigator may repeat the ECG to verify the results of the original result). If the ECG result is determined to be a clinically significant and abnormal change from baseline for that subject, this is considered an AE.

6.6 Diet and Exercise Counseling

Subjects will receive counseling regarding an appropriate diet and exercise to aid in glycemic control based on standards of medical care in diabetes throughout the study. In addition, all subjects are encouraged to consume enough non-sweetened liquids to maintain adequate hydration.

6.7 Clinical Laboratory Tests

6.7.1 Laboratory Parameters

Subjects will be in a seated or supine position during blood collection. Each laboratory test is outlined in Table 1 and the schedule is provided in [Appendix 1](#).

Table 1. List of Laboratory Tests

Test Name	Blood or urine Vol. (mL)	Shipment
Hematology¹	2 (blood)	Ambient
- Hematocrit (Hct)	- Mean corpuscular volume (MCV)	
- Hemoglobin (Hgb)	- Platelet count	
- Mean corpuscular hemoglobin (MCH)	- Red blood cell (RBC) count	
- Mean corpuscular hemoglobin concentration (MCHC)	- White blood cell (WBC) count with differential	
Serum Chemistry and Electrolytes^{1,2}	10 (serum)	Ambient
- Albumin (ALB)	- Calcium (Ca)	
- Alanine aminotransferase (ALT)	- Magnesium	
- Aspartate aminotransferase (AST)	- Phosphorus	
- Blood urea nitrogen (BUN)	- Potassium (K)	
- Glucose	- Sodium (Na)	
- Bicarbonate (HCO ₃)	- Total bilirubin	
- Creatinine Chloride (Cl)	- Direct bilirubin	
- Total protein	- Uric acid	
Glycemic Control,¹		Ambient
- Fasting plasma glucose (FPG)	2 (plasma)	
- Hemoglobin A1c (HbA1c)	2 (blood)	
Serum Lipids^{1,3}	6 (serum)	Ambient
- Total cholesterol (TC)	- Low-density lipoprotein cholesterol (LDL-C), calculated	
- High-density lipoprotein cholesterol (HDL-C)	- LDL-C, direct ⁵	
- Triglycerides (TG)		
Urinalysis⁴	10 (urine)	Ambient
- Appearance	- Nitrite	
- Bilirubin	- Occult blood	
- Color	- pH	
- Glucose	- Protein	
- Ketones	- Specific gravity	
	- Urobilinogen	
	- Leukocyte esterase	
Urine drug screen⁵	10 (urine)	Ambient
- Amphetamines	- Opiates	
- Barbiturates	- Benzodiazepines	
- Cocaine Metabolites	- Cannabinoids	
Infectious Disease Testing⁶	6 (serum)	
- HBsAg	- HCV	
Urine pregnancy test (WOCBP) ⁷	2 (urine)	Local
Population PK Sampling⁸	6 (plasma)	Frozen
- Bexagliflozin plasma level		

1. Blood for clinical chemistry and hematology will be drawn after at least 10 h of fasting prior to breakfast (i.e. only water is allowed, no caloric intake).

2. Lactate dehydrogenase (LDH), gamma-glutamyl transferase (γ -GTP), creatinine kinase (CK),

Test Name	Blood or urine Vol. (mL)	Shipment
and alkaline phosphatase (ALP) are not required routinely but will be included when clinically indicated.		

 
3. LDL-C will be calculated by the Friedewald equation. If triglycerides are > 400 mg/dL, the calculated LDL-C value is invalid by this equation and will be set as missing. Direct LDL-C will be determined in subjects whose baseline triglycerides are > 300 mg/dL. All subsequent LDL-C of these subjects will be determined by the same direct LDL-C measurements only. 
4. Urinalysis will be collected routinely at all clinic visits except S3 and V1 from a clean catch sample. Glucose results in the urinalysis reports must be suppressed so the dosing blind can be maintained. Testing strips with only the leucocytes and nitrate will be provided for immediate assessment at the clinical sites. 
5. Urine drug screen will be performed on screening visit only. Drug abuse screening includes amphetamines, barbiturates, cocaine metabolites, opiates, benzodiazepines, and cannabinoids. 
6. Infectious disease testing will be conducted at screening only. 
7. Urine pregnancy test (UPT) will be performed for WOCBP at all clinic visits, except Visits S3 and V1. For surgically sterile or post- menopausal women, it will only be done at Visit S1. 
8. Blood samples for the population PK analysis will be drawn at or during the weeks of V2, V3 or V4 from 240 randomly selected subjects in participating trial centers. 		

6.7.2 Sample Collection, Storage, and Shipping

6.7.2.1 Hematology, Blood Chemistry, Serum Lipids, and Glycemic Control Assessments

Blood samples for hematology, chemistry, serum lipids and glycemic control assessments will be collected. Timing of collection is described in [Section 7](#) and the Schedule of Events (see [Appendix 1](#) and [Appendix 2](#)).

The study staff will contact each subject prior to a scheduled clinic visit to confirm the time of the visit and to remind the subject of the proper fasting procedure. A subject must be queried to assess compliance with a minimum 10 h fast prior to blood draw to ensure the FPG and triglycerides values can be accurately determined. If a subject has not fasted for at least 10 h, the subject must return as soon as can be arranged (within 7 days) to provide a specimen after proper fasting. If the 10 h fasting sample is not collected within 7 days of the initially scheduled visit, the FPG will be considered missing.

6.7.3 Urinalysis

Urine samples will be collected per the schedule outlined in [Section 7](#).

Investigator or staff should document if pre-menopausal female subjects are menstruating and note it in the source documents since hematuria is likely to be identified on dipstick urinalysis.

Urinalysis strips that assess leukocyte esterase and nitrite and that do not report the presence or absence of glucose will be provided for immediate assessment at the clinical sites. Urine samples will also be transported to the central laboratory.

Urine culture and microscopy will be conducted at the central lab if the subject has a positive result on the leukocyte esterase or nitrite dipstick tests at the clinical site. Dipstick urinalysis will also be conducted at the central laboratory for assessment of parameters not measured at the clinical site. Positive leukocyte esterase or nitrite results recorded from the central laboratory dipstick measurement will not trigger urine culture and microscopy.

6.7.4 Population PK Sampling

Blood samples for the population PK analysis will be drawn when the subjects return to the clinic during weeks 2, 6, or 12 from 240 selected subjects in participating trial centers. One blood sample will be drawn at each of the 3 time points from each subject for a total of 3 postdose samples per subject. Approximately 120 subjects will be sampled at 0.25-1 h, 7-10 h, and 20-24 h post dose. Another 120 subjects will be sampled at 1.5-3 h, 3.5-6.5 h and 7-10 h postdose. The sampling time should take into consideration the study subject availability and can be on any of the days during the week of the specified clinical visits. The precise dosing time and sample draw time must be recorded.

Two mL (2 mL) of whole venous blood will be collected from a peripheral vein. Samples will be placed in tubes containing K₂EDTA, stored on ice, and centrifuged under refrigeration for at least ten minutes at 3,000 rpm. After centrifugation, plasma will be removed and stored frozen in 3 aliquots of 200 µL at or below -20° C. Processed frozen plasma samples will be transferred on dry ice to the analytical laboratory and will be stored at or below -20° C until analysis.

Plasma concentrations of bexagliflozin will be determined by a validated LC-MS/MS method. Approximately 540 measurements of bexagliflozin plasma concentrations will be collected from an estimated 180 subjects who will have received active drug in this study.

6.8 Dispensing Investigational product

Each study subject will receive 1 run-in kit at visit S4 and 1 investigational product kit at visits V1 (week 1).

6.9 Efficacy Assessments

6.9.1 HbA1c Determination

The HbA1c values will be determined in a central laboratory using a method that is certified by the National Glycohemoglobin Standardization Program (NGSP) and standardized to the Diabetes Control and Complications Trial (DCCT) reference assay.

6.9.2 Body Weight

Total body weight will be determined in clinical visits as described in Section 6.3.

6.9.3 Blood Pressure

Systolic and diastolic blood pressure will be determined as described in the vital signs section (Section 6.4).

6.10 Adverse Events Assessments

Adverse event (AE): Any untoward medical occurrence experienced by a subject administered an investigational product. An AE does not necessarily have a causal relationship with treatment. An AE can therefore be any unfavorable and unintended accident, sign (including an abnormal laboratory finding), symptom, or disease occurring during the period of use of an investigational product or the period of follow-up, whether or not related to the investigational product.

Serious adverse event (SAE): Any event that results in any of the following outcomes:

1. Death
2. A life-threatening event, *i.e.*, the subject was, in the opinion of the investigator, at immediate risk of death from the event as it occurred (this does not include an event that, had it occurred in a more severe form, might have caused death)
3. A persistent or significant disability/incapacity
4. An event that requires hospitalization or prolongs hospitalization
5. A congenital anomaly/birth defect
6. Any other medically significant events that, based upon appropriate medical judgment, may harm the subject and may require medical or surgical intervention to prevent one of the outcomes listed above, *e.g.* allergic bronchospasm requiring intensive treatment in an emergency room or home; blood dyscrasias or convulsions that do not result in hospitalization; or the development of drug dependency or drug abuse.

Non-serious adverse events are all events that do not meet the criteria for a serious adverse event.

Immediately Reportable Adverse Event (IRAE): Any serious adverse event or any adverse event that necessitates discontinuation of investigational product, including pregnancy.

Clinical Laboratory Changes: It is the investigator's responsibility to review the results of all laboratory tests as they become available. For each abnormal laboratory test result the investigator needs to ascertain if this is a clinically significant change from baseline for that individual subject (this determination, however, does not necessarily need to be made the first time an abnormal value is observed. The investigator may repeat the laboratory test or request additional tests to verify the results of the original laboratory tests). If the laboratory

value is determined to be a clinically significant and abnormal change from baseline for that subject, this is considered an AE.

Hypoglycemia is defined as any FPG or SMBG value ≤ 70 mg/dL and documented as described in [Section 6.10.9](#).

Any increase in liver function tests (AST, ALT, or bilirubin) greater than 3 times the ULN for the laboratory utilized will be considered a clinical laboratory adverse event.

Severity: Adverse events will be graded on a 3-point scale and reported as indicated on the CRF. The intensity of an adverse experience is defined as follows:

1 = Mild: discomfort noticed, but no disruption to daily activity;

2 = Moderate: discomfort sufficient to reduce or affect normal daily activity;

3 = Severe: inability to work or perform normal daily activity.

Investigational Product Causality: An assignment made by the investigator based on the circumstances of the event and its analysis. Cases with causal relationship classified as possible, probable or definite are defined as related. Cases with causal relationship categorized as not likely or unrelated are defined as not related. Relationship of an adverse event to dosing will be assessed as follows:

Definite: The event responds to withdrawal of the investigational product (dechallenge), and recurs with rechallenge by administration of the investigational product.

Probable: There is a reasonable causal relationship between the investigational product and the AE. The event responds to dechallenge. Rechallenge is not required.

Possible: There is a reasonable causal relationship between the investigational product and the AE. Dechallenge is lacking or unclear.

Not Likely: There is a temporal relationship to investigational product administration, but there is not a reasonable causal relationship between the investigational product and the event.

Unrelated: There is not a temporal or causal relationship to investigational product administration.

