6.10.8 Hepatotoxicity

If plasma AST and/or ALT concentrations $> 3 \times$ ULN are detected, the investigator will record in the source documents the date corresponding to the date of the laboratory abnormality; the type, frequency, and dose of any concurrent medications or supplements taken by the subject within the 14 days of the detected abnormality; and any symptoms or change in physical exam that have occurred since the prior assessment. The investigator should perform additional laboratory and imaging tests to attempt to establish the cause of the AST and ALT elevations, including ruling out any potential contribution from bone or muscle etiologies.

Any clinically significant increase in hepatic enzymes and specifically any ALT or AST $> 3 \times$ ULN requires immediate repeat test within 48 to 72 h to confirm the hepatic enzyme elevation and should be repeated based on the clinical situation at least every 96 h (4 days) until ALT and AST return to $< 2.5 \times$ ULN. Study medication should be stopped and the event should be reported as a laboratory adverse event within the CRF if the enzyme elevation is confirmed or worsening.

Hepatotoxicity will be diagnosed and entered as an AE should any of the following occur:

- ALT or AST $> 8 \times$ ULN;
- ALT or AST $> 3 \times$ ULN and total bilirubin $> 2 \times$ ULN or INR > 1.5
- ALT or AST $> 3 \times$ ULN with the appearance of fatigue, nausea, vomiting, right upper quadrant pain or tenderness, fever, rash, and/or eosinophilia ($> 5\%$).

In the event of hepatotoxicity, investigational product should be permanently discontinued. The investigator is encouraged to consult with the Medical Monitor regarding diagnostic evaluation for the hepatic enzyme elevations. Consultation with a hepatologist may also be appropriate in some circumstances.

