3.9.1.6 AEs of Special Interest

Adverse events of special interest include the following categories:

- Genital mycotic infections
- Urinary tract infections including urosepsis and pyelonephritis
- Diuretic effects including hypovolemia
- Hypotension episodes
- Hepatotoxicity
- Major Adverse Cardiovascular Event (MACE)
- Hypoglycemia
- Falls and fractures
- Malignancies
- Hypersensitivity reactions
- Acid-base disorders
- Renal failure events

All AEs of special interest will be identified by appropriate MedDRA preferred term during a blinded review of the data.

The incidence of TEAEs of special interest by treatment group and for all active treatment groups combined will be presented separately for each category. The number and percentage of subjects who experienced at least one TEAE of special interest as well as the number and percentage of subjects who experienced each specific SOC and PT will be presented. For this analysis, if a subject has more than one occurrence of the same PT, then the PT will be counted only once for that subject. Similarly, if a subject has more than one occurrence of the same PT within a SOC, the subject will be counted only once in that SOC.

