Continuous laboratory data will be examined for trends using descriptive statistics of changes from baseline to each planned post-baseline visit. These data will also be categorized as low, normal or high based on the reference ranges of the central laboratory. The number and percentage of subjects with indicated shifts relative to the laboratory normal ranges (low, normal, high) in their results from baseline to each post-baseline visit will be presented by category for all applicable laboratory parameters listed in Table 3. The analyses will be performed using the safety analysis set and presented by treatment group.

A separate listing for all clinically significant laboratory abnormalities will be provided.

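### Protocol 6.10 and 6.10.8 differ on recording an unconfirmed ALT or AST above 3 x ULN, and no planned by-arm table counts subjects at the protocol's own hepatic thresholds

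*Protocol*

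**What the plan says.** **Recording rules.** Protocol 6.10 states without further condition that an AST, ALT or bilirubin increase "greater than 3 times the ULN for the laboratory utilized will be considered a clinical laboratory adverse event". The general laboratory rule before it depends on the investigator's view of clinical significance and lets that view wait for a repeat: "this determination, however, does not necessarily need to be made the first time an abnormal value is observed".

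Protocol 6.10.8 covers AST and ALT. A value above 3 x ULN "requires immediate repeat test within 48 to 72 h to confirm the hepatic enzyme elevation". Then, in a sentence that also deals with stopping study medication, it says that "the event should be reported as a laboratory adverse event within the CRF if the enzyme elevation is confirmed or worsening". A separate diagnosis follows: "Hepatotoxicity will be diagnosed and entered as an AE should any of the following occur". The criteria are ALT or AST above 8 x ULN; above 3 x ULN with total bilirubin above 2 x ULN or INR above 1.5; and above 3 x ULN with listed symptoms or eosinophilia.

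**Analysis.** Hepatotoxicity is an event category of special interest. SAP 3.9.1.6 finds such events from coded AEs: "All AEs of special interest will be identified by appropriate MedDRA preferred term during a blinded review of the data". SAP 3.9.2 summarises laboratory data as change from baseline and as shifts: "These data will also be categorized as low, normal or high based on the reference ranges of the central laboratory". It adds a listing of clinically significant abnormalities, and SAP 5.3 lists individual chemistry values by subject.

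**The concern.** Take an asymptomatic subject whose ALT is above 3 x ULN once and lower on repeat. Section 6.10 makes that value a laboratory AE. Section 6.10.8 attaches its reporting instruction to confirmation or worsening, and here neither occurs. Two sites following the protocol in good faith can record this subject differently.

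This would matter little if the planned laboratory output gave an independent count. It does not. The AE and special-interest tables start from what sites entered, and the shift tables do not use the multiples of ULN on which 6.10.8 bases repeat testing and the hepatotoxicity diagnosis. In a dose-finding trial, the by-arm comparison for a named safety category would then have no objective count beside it.

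**Working it through.** No figure in the plan bears on this point, so there is none to reproduce.

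**Step 1: which values are recorded differently.** Example profiles, each without symptoms, eosinophilia or raised INR, and with normal bilirubin unless stated:

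| Profile | AE under 6.10 | Laboratory AE called for by 6.10.8 | Hepatotoxicity AE under 6.10.8 | ALT shift cell in SAP |
|---|---|---|---|---|
| ALT 3.5 x ULN, repeat 1.5 x | yes | no | no | high |
| ALT 3.5 x, repeat 3.6 x | yes | yes | no | high |
| ALT 9 x, repeat 2 x | yes | no | yes | high |
| Bilirubin 3.2 x, ALT normal | yes | not addressed | no | normal |
| ALT 1.1 x | no | no | no | high |

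Only the first row is an AE under one section and not the other. The third is an AE either way because of the 8 x criterion. The fourth has one governing rule, that of 6.10. The disputed group is therefore unconfirmed ALT or AST above 3 x and up to 8 x ULN that meets none of the combined criteria.

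**Step 2: what the laboratory tables can show.** ALT of 1.1 x, 3.5 x and 9 x ULN falls in the same cell. Shifts are made parameter by parameter, so ALT with bilirubin cannot be read jointly. No table or figure title in SAP 5.1 and 5.2 refers to a multiple of ULN.

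The SAP 3.1.9 windows are Days 8-22, 36-50, 78-92 and 93-105, which leaves Days 2-7, 23-35 and 51-77 uncovered. Within a window the record closest to the target day is used. Suppose the Week 2 visit is on Day 15:

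- A repeat after 48 to 72 h falls on Day 17 or 18. It is inside the window, but the Day 15 value is kept.
- A further test four days after Day 18 falls on Day 22. It is inside the window and again not kept.
- The next falls on Day 26, in no window.

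A peak on any of these repeats is absent from the by-visit summaries. Only an early termination visit outside the windows is carried to the next time point. Protocol Appendix 2 schedules chemistry after randomization only at Weeks 2, 12 and 14, so values between Weeks 2 and 12 are unscheduled.

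**Step 3: size.** With 80 subjects per arm, one subject is 1/80 = 1.25 percentage points. The documents give no rate of elevations and no confirmation rate. For illustration only, let p be the share of subjects with ALT or AST above 3 x ULN and c the share of these that are confirmed. If all sites followed 6.10.8 instead of 6.10, the expected number recorded differently per arm is 80 x p x (1 - c):

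- p = 0.5%, c = 75%: 80 x 0.005 x 0.25 = 0.1
- p = 1%, c = 50%: 80 x 0.01 x 0.50 = 0.4
- p = 3%, c = 25%: 80 x 0.03 x 0.75 = 1.8

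In the 240 active subjects, the middle case gives 240 x 0.01 = 2.4 expected events under 6.10 and 2.4 x 0.50 = 1.2 under 6.10.8. The chance of at least one event is 1 - 0.99^240 = 0.91 against 1 - 0.995^240 = 0.70. These figures are high for the assumed rates, because they ignore unconfirmed values that meet a hepatotoxicity criterion and assume that every site switches rule.

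**The case against.** The strongest reply is that the sections can be read together. Section 6.10.8 says if, not only if. Its sentence can describe what follows confirmation without cancelling 6.10, and the general laboratory rule allows a repeat before judgment. This stands in part: the wording is ambiguous, not two mutually exclusive rules. But nothing tells sites to combine the sections, and the 3 x ULN sentence in 6.10 has no exception for unconfirmed values.

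Second, objective data are planned. Descriptive statistics include the maximum, so a visit maximum below 3 x ULN settles that arm and visit for the records selected. Every value is listed, and unblinded ALT and AST tables go to the monitoring committee. This also stands, with limits. A maximum above the threshold does not say how many subjects exceeded it, and repeats can be lost as shown. The committee's laboratory tables omit bilirubin (SAP 5.1 footnote), and the laboratory listings are not marked for it (SAP 5.3). Threshold counts could be derived from the data, but none is planned.

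Third, the protocol promised low/normal/high shifts and the SAP delivers them, so the missing threshold table contradicts nothing. That is right: the table is an addition that removes a dependence, not the repair of a breach. Fourth, screening excludes ALT or AST at or above 2.5 x ULN, so events may be few. That too is fair, and it is one reason for claiming no size.

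**Conclusion.** The point holds in a narrow form. Sites may differ on asymptomatic, unconfirmed ALT or AST elevations above 3 x ULN that meet no hepatotoxicity criterion, and no planned by-arm laboratory count is independent of that choice.

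Four stronger inferences are tempting, and the documents do not support them:

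- *The whole hepatic result turns on the site's reading.* Confirmed elevations and those meeting the hepatotoxicity criteria are AEs either way, individual values are listed, and preferred terms for the special-interest category are chosen in a blinded data review.
- *Bilirubin rules conflict.* Section 6.10.8 is silent on isolated bilirubin above 3 x ULN, so 6.10 alone applies.
- *The comparison is biased toward an arm.* Investigators are blinded. Mixed recording mainly shifts absolute incidence and comparability between sites; it would favour an arm only if confirmation rates differed by arm.
- *Several subjects per arm would be affected.* No document gives a rate. The 0.1 to 1.8 subjects per arm shown above rests wholly on assumed rates.

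**What to change.** 1. The sponsor should reconcile Protocol 6.10 and 6.10.8 into one AE-recording rule for ALT or AST above 3 x ULN. This review does not say which rule is right. Because 6.10.8 joins reporting and stopping of study medication in one sentence, the rewording needs care; no change to stopping rules is proposed.
2. In SAP 3.9.2, add one by-arm table for the safety analysis set, from central-laboratory data, using all post-baseline values including unscheduled repeats and not only those selected by visit window. Give the number and percentage of subjects with:
   - ALT or AST above 3 x ULN
   - ALT or AST above 8 x ULN
   - total bilirubin above 2 x ULN
   - ALT or AST above 3 x ULN with total bilirubin above 2 x ULN, stating how close in time the two must be

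INR is not in either document's laboratory list, so that criterion is left out. The cost is one wording change and one more table from data already collected.
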